The primary cervical elasticity assessment currently used in clinical practice is relying on the clinician's evaluation of the cervix as "hard, medium or soft" which is descriptive and subjective. Clinicians use terms such as *softening*, *shortening*, *funneling*, *effacing*, and *dilating* to describe changes in the cervical conditions that occur during pregnancy. Collectively, these changes are called *cervical remodeling* and refer to both the tissue's intrinsic material property changes and its resultant anatomical changes. These changes definitely require objective and reliable quantification.

In the scope of this project we propose to develop and clinically validate a new and cost-effective device, Cervix Monitor (CM), for detecting cervix conditions leading to SPTD and its risk assessment. The CM will be based on measuring of the applied pressure to the cervix by a tactile sensor array (stress data) and ultrasound measurement of cervix length (strain data). Tactile and ultrasound sensors will be allocated on the tip of the disposable measuring part of vaginal probe (see Figure 1). Both stress and strain data will allow cervix elasticity and effacement evaluation. The discovery of novel biomarkers that could reliably identify women who will subsequently deliver preterm, may allow for timely medical intervention and targeted therapeutic treatments aimed at improving maternal and fetal outcomes.

**Figure 1.** Concept of proposed cervix monitor. It will allow elasticity and length measurements of the uterine cervix during gestation to explore and detect conditions leading to spontaneous preterm delivery.

The objectives of the Phase I research, which covers the proposed protocol, are listed below.

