### Subjects

The study will involve 10 non-pregnant, 2 CM measurements per subject. Adult non-pregnant pre-menopausal women scheduled for a regular gynecological examination at Princeton Urogynecology (Princeton, NJ) will be considered eligible for enrollment into the study. Each patient will first be studied with the existing clinical means and then with the CM. A clinical research assistant will maintain a log as to any concerns/complications with the CM.

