## **Methods and Procedures**

The examination procedure will comprise the steps of:

1. Inserting the speculum into the vagina to provide appropriate visualization and access to the cervix.
2. Performing CM measurements at 3, 6, 9, and 12 o'clock specifying the probe tip location on cervix on the touch screen display.
3. Review the measurement results (elasticity and length values) and repeat two measurements, one at the location with the lowest elasticity and one at the location with highest value.
4. Removing the probe and speculum from the vagina.

This CM examination procedure will be explored and further optimized based on the practical experience.

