## **Data Analysis**

Measurement repeatability between two measurements will be assessed with a reliability parameter, which is also known as an intraclass correlation (ICC), as it equals the correlation between any two measurements made on the same subject. The difference between pairs of measurements will be plotted against their mean in a Bland-Altman plot. The average difference between measurements will be calculated as well as the 95% limits of agreement (LOA).

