## **Study End Points**

Study end points (measures that will be considered as success):

1. The examination using CM is safe, does not cause significant discomfort and is capable of production of expected measurement results.
2. The CM elasticity measurements have intraoperator ICC of 0.90 or above; 95% LOA is within  $\pm 15\%$ .
3. The CM cervix length measurements have intraoperator ICC of 0.93 or above; 95% LOA is within  $\pm 10\%$ .

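### Repeats are taken only where the first elasticity reading was lowest or highest, after the values are seen, so the elasticity ICC and limits of agreement would not measure repeatability at a given position

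*Combined protocol and SAP*

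**What the plan says.** Methods and Procedures takes one reading at each of four clock positions. Step 3 then tells the operator to "Review the measurement results (elasticity and length values" and to "repeat two measurements, one at the location with the lowest elasticity and one at the location with highest value". That makes six readings per woman, of which two are repeats. The section closes with "This CM examination procedure will be explored and further optimized based on the practical experience".

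Other sections bear on this:

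- Subjects: "The study will involve 10 non-pregnant, 2 CM measurements per subject". What counts as a measurement is not defined, and the figure does not match six readings.
- Data Analysis: an ICC, and "The difference between pairs of measurements will be plotted against their mean in a Bland-Altman plot", followed by the average difference and 95% limits of agreement. It does not say which pairs are used and makes no allowance for how the sites were chosen.
- Study End Points, item 2: "The CM elasticity measurements have intraoperator ICC of 0.90 or above; 95% LOA is within" ±15%. Item 3: "The CM cervix length measurements have intraoperator ICC of 0.93 or above", with limits within ±10%.

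No second four-position examination is described, so the step 3 repeats are the only same-position pairs in the plan.

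**The concern.** A repeatability estimate needs pairs in which the first reading's error is a random draw. Here a site is repeated because its first reading was the smallest or largest of four. On average, the error of a chosen low reading is negative and that of a chosen high reading is positive, so the repeat regresses towards the middle.

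This has three consequences for elasticity:

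- The two offsets have opposite signs and cancel in the pooled average difference. That is the only summary of bias planned, so a value near zero would be false reassurance.
- The offsets widen the limits of agreement.
- Taking the two most different sites changes the spread between pairs, which moves the ICC down or up depending on how much positions truly differ.

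Sites are not chosen on length, so selection should matter little for length. Length shares a second problem with elasticity: the operator has seen the first values before repeating, and this can favour agreement.

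At stake is the reading of a numeric success criterion. A pass or a fail would mix device repeatability with the effect of the selection rule.

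**Working it through.** The plan gives no variance, power or precision figure, so there is nothing to reproduce. The inputs from the documents are 10 women, 4 positions, 2 repeats per woman (20 pairs) and the thresholds. Everything else is assumed.

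**Model.** Reading = 100 + woman + position + error, all normal, with variances sW², sL² and se². With se = 5.41 the true limits are 1.96 × 5.41 × √2 = ±15.0, that is ±15% of the mean. A true ICC of 0.90 means sW² + sL² = 9 se². The position share is sL² / (sW² + sL²).

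**Large-sample effect.** For four normal values, the expected maximum is 1.029 SD and its mean square is 1.55. Let k = se² / (sL² + se²). Then, for pairs at the lowest and highest first reading:

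- Offset at each extreme = 1.029 se² / √(sL² + se²)
- Variance of the pooled differences = se² (2 + 0.55k)
- ICC = C / (C + W), where C = sW² + 1.55 sL² and W = se² (1 + 0.275k), half the variance of the differences

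Worked case, share 0: k = 1, and the offset is 1.029 × 5.41 = 5.57. The limits are 1.96 × 5.41 × √2.55 = ±16.9. The ICC is 9 / (9 + 1.275) = 0.876.

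Worked case, share 50%: sL² = 4.5 se² and k = 1/5.5 = 0.182. The offset is 5.57 / √5.5 = 2.4. The limits are 1.96 × 5.41 × √2.10 = ±15.4. With C = 4.5 + 1.55 × 4.5 = 11.475 and W = 1.05, the ICC is 0.916.

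| Position share | Offset (% of mean) | Limits (true ±15.0%) | ICC (true 0.900) |
|---|---|---|---|
| 0 | 5.6 | ±16.9 | 0.876 |
| 25% | 3.1 | ±15.6 | 0.904 |
| 50% | 2.4 | ±15.4 | 0.916 |
| 75% | 2.0 | ±15.3 | 0.925 |
| 100% | 1.8 | ±15.2 | 0.931 |

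With positions fixed in advance, the large-sample values equal the true ones. Simulation agrees with the table.

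**Chance of passing with 20 pairs.** This is a simulation of 40,000 trials per scenario, with a one-way ICC and limits = mean difference ± 1.96 SD. A pass needs ICC at least 0.90 and both limits within ±15. Independent re-runs agree within about one percentage point. Entries are selected sites against fixed sites.

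| Position share | True ICC 0.90, limits ±15% | True ICC 0.90, limits ±11% |
|---|---|---|
| 0 | 8% v 23% | 27% v 43% |
| 25% | 23% v 25% | 50% v 45% |
| 50% | 28% v 26% | 67% v 47% |
| 75% | 30% v 27% | 78% v 48% |

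Other true ICC values:

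- True ICC 0.85 (below the plan's threshold), 75% share: 24% v 14% with limits ±15%, and 38% v 17% with ±11%. At a 25% share: 11% v 12% and 17% v 17%.
- True ICC 0.93, limits ±15%: 27% v 31% (25% share), 31% v 32% (50%) and 31% v 32% (75%). With limits ±11% and a 50% share: 88% v 74%.

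**Length.** If length and elasticity errors are unrelated, choosing sites on elasticity gives no offset and leaves the length limits unchanged. A link cannot be excluded, because the Introduction says "Both stress and strain data will allow cervix elasticity and effacement evaluation" and the strain data are the length measurements. At an assumed error correlation of 0.5, true limits of ±10.0% become only ±10.1% to ±10.3%.

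**Seeing the first values.** The size is unknown. As illustration only, if the repeat's error is pulled a fraction l towards the first, the limits shrink by (1 − l). With l = 10%, true limits of ±11.1% would show as 11.1 × 0.9 = ±10%.

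**The case against.** Four points can be made for the plan.

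First, no section says outright that the step 3 pairs are the ones analysed. If two measurements per subject meant two full examinations, unselected pairs would exist. This stands as a caveat, but no second examination is described.

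Second, the distortion is often smaller than sampling noise. With 20 pairs and an SD of differences of 5.41 × √2 = 7.65, the standard error of one limit is about 7.65 × √(1/20 + 1.96²/38) = 3.0 points. Selection moves the limit by 0.4 points at a 50% share and by 1.9 at worst, always in the conservative direction. The ICC moves by about 0.025 at shares of 0 and 75%, against a sampling SD of 0.05 to 0.08 with fixed sites. This also stands, and several scenarios show pass rates only 1 to 4 points apart. It does not settle the matter: the shift is systematic, and in other plausible scenarios the gap is 15 to 30 points.

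Third, this is a pilot in 10 women meant to try out the procedure, and repeating at the extremes covers the measured range. That limits the consequences. But the pilot sets numeric success criteria, and the section on the importance of the knowledge to be gained makes the larger studies in pregnant women follow from meeting its milestones.

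Fourth, the length and unmasking figures rest on arbitrary inputs. Agreed: for length the point is qualitative.

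**Conclusion.** The concern holds and should be fixed, with medium confidence. If the step 3 pairs are analysed, as the text implies, the elasticity ICC and limits of agreement describe selected extremes and not repeatability at a given position. At an assumed true ICC of 0.90 and true limits of ±15%, the opposite offsets are 1.8% to 5.6% of the mean and invisible in the pooled average difference. The limits widen by 0.2 to 1.9 points. The ICC shifts by between −0.024 and +0.031.

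The chance of meeting end point 2 can fall by about 15 points or rise by about 30. At a true ICC of 0.85 it can more than double (38% against 17%). The net direction depends on position differences and true limits that the documents do not give, so the rule should not be called simply optimistic or pessimistic. For length, selection bias is small or nil. The effect of seeing the first values cannot be sized for either measure.

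**What to change.** 1. Rewrite step 3 so that the two repeats are at clock positions set beforehand, fixed or from a random list prepared before the study, whatever the first readings show. Hide or cover the elasticity and length values until all six readings are stored, showing only that a reading was captured. Review them afterwards.
2. In Data Analysis, state that the two first/repeat pairs per woman (20 pairs from 10 women) are analysed, and how two pairs from the same woman are handled. Reconcile the two measurements per subject in Subjects with the six readings in Methods and Procedures.
3. If the procedure is changed during the pilot, record the change. Compute end points 2 and 3 only from women examined under the pre-set procedure, and report how many that is.
4. Identify the extremes afterwards from the stored data. If they are kept as repeat sites, report low-site and high-site differences separately and do not rely on the pooled average.

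The cost is one rewritten step and a few sentences, with readings per woman unchanged at six. The softest site will not always be repeated. The display may need a cover or a small change, since the documents do not say that the software can hide values. Repeating all four positions would also remove the selection and always include the softest site, at the price of two more readings (eight in all).

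None of this cures the imprecision of 20 pairs: a device exactly at ICC 0.90 and limits of ±15% would still pass only about 23% to 27% of the time with fixed sites.

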## **Protection of Human Subjects**

### Human Subjects Involvement, Characteristics and Design

Adult non-pregnant women scheduled for a regular gynecological examination at Princeton Urogynecology (Princeton, NJ) will be considered eligible for enrollment into the study with Cervix Monitor (CM). Conditions precluding patients from participation are listed in the study exclusion criteria below. This study with non-pregnant women is conducted to assess potential risks to pregnant women and fetuses as required by Code of Federal Regulations, Title 45, §46.204(a). This study with non-pregnant women will be conducted before initiation the study with pregnant women.

The highest priority will be given to consideration of examination safety with CM probe, disturbing the cervix tissue during pregnancy and potential risk of premature delivery, infection or miscarriage. Clinical study coordinators will maintain a log as to any concerns, complications, or suggested improvements in using the CM probe. After the CM examination a questionnaire will be presented to patients to assess their comfort and pain concerns relative to the procedure. All clinical investigators will have their CV on file with the local IRB and complete training and certification in Protecting Human Research Participant. Explanation of how data from the sites will be obtained, managed, and protected is presented in Data and Safety Monitoring Plan section (see below).

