### Source of Materials

Upon patient's consent, relevant clinical and demographical data will be collected. Specifically, obstetrical history, course of the previous current pregnancy(s), history of prior surgery and a connective tissue disorders (i.e. Ehlers-Danlos Syndrome, Benign Joint Hypermobility Disorder, etc.), race, age, height, weight, and parity will be documented.

Prior to taking the CM scan, standard obstetric external and internal vaginal examination will be performed by a clinical investigator. Attention to cervix softness, elasticity and any abnormalities

will be made and the results recorded to map the cervix surface. A 4-point grading system for cervix elasticity would be giving soft (0), or moderately soft (1), or moderately stiff (2), or stiff (3) elasticity scores to cervix. These subjective measurements would then be correlated with the CM data for agreement or discordance.

The CM examination will be performed as described above in Methods and Procedures section. The process is quick, non-invasive and should cause no additional discomfort to the patient as compared to a standard pelvic examination. All results will be recorded using an examination chart, which will be a part of the Case Report Form (CRF) specifically designed for the study. The chart will summarize all findings by all mean to characterize the cervix in terms of appearance and elasticity.

All necessary clinical and demographic data will be derived from existing records and de-identified. No additional clinical tests will be ordered to support this research. A specific clinical study number will be generated for each examination case so the link between the data and the patient will be created without revealing patient identity.

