#### Potential Risks

Investigators do not expect any additional risks or side effects from the use of CM beyond those normally associated with standard manual palpation and transvaginal ultrasound, such as extremely rare possibility of physical damage of the vagina, cervix tissue and infection. Other risks include software/hardware malfunction, toxicity, allergic reaction, electrical shock and breach of confidentiality.

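### Tissue damage is a named risk, but the procedure specifies no look at the contact sites before the speculum comes out, so minor symptomless injury can go unrecorded

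*Combined protocol and SAP*

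**What the plan says.** **Purpose.** Study Objectives puts the assessment of risk to pregnant women and fetuses first, using non-pregnant women. Study End Points makes safety of the examination part of the first success criterion, without defining it. Human Subjects Involvement, Characteristics and Design says: "The highest priority will be given to consideration of examination safety with CM probe, disturbing the cervix tissue during pregnancy". It also places this study before any study in pregnant women.

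**Named risk.** Potential Risks lists an "extremely rare possibility of physical damage of the vagina, cervix tissue and infection".

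**Procedure.** Step 1 of Methods and Procedures is "Inserting the speculum into the vagina to provide appropriate visualization and access to the cervix". Step 2 takes readings at four clock positions. Step 3 is to "Review the measurement results (elasticity and length values) and repeat two measurements", at the positions with the lowest and highest elasticity. Step 4 is "Removing the probe and speculum from the vagina".

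**Examination and chart.** Under Source of Materials, "Prior to taking the CM scan, standard obstetric external and internal vaginal examination will be performed by a clinical investigator". That examination notes abnormalities and maps the surface of the cervix. The same section describes a CRF chart: "The chart will summarize all findings by all mean to characterize the cervix in terms of appearance and elasticity".

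**Safety capture after the scan.** There are three sources: a log of problems (Subjects; Human Subjects Involvement, Characteristics and Design), a patient questionnaire on comfort and pain (Data Collection; Human Subjects Involvement, Characteristics and Design), and reporting of adverse events by investigators (Data and Safety Monitoring Plan).

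**The concern.** Non-pregnant women cannot show miscarriage or preterm delivery. Local effect on tissue is one of the few direct safety outcomes that they can supply for the first objective. As written, the plan gathers it passively. The questionnaire records what a woman feels. The log and the adverse event reports record what staff happen to notice. A small abrasion or slight contact bleeding that causes no symptoms need not reach any of them.

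The final report could then state that no injury was recorded without a reader knowing whether anyone had looked. That statement would support the first end point and would be available when the later study in pregnant women is considered.

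**Working it through.** The plan states no figure on this point, so there is none to reproduce. The check is mainly a comparison of sections.

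**1. Is a post-contact inspection specified anywhere?**
- *Methods and Procedures:* no. What is reviewed in step 3 is the elasticity and length values, not the tissue. Step 4 is removal.
- *Source of Materials:* the clinical examination comes before the scan. The chart includes appearance, but nothing ties that entry to a look after contact or to injury.
- *Data Collection:* no tissue finding is listed.
- *Protection Against Risks:* training, use of a speculum and feedback from the probe are given as ways to reduce injury, not to detect it.
- *Data and Safety Monitoring Plan:* events that occur are to be reported and categorized. No method of looking for them is stated.
- No post-scan examination or follow-up contact is described in any section.

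**2. Is there a baseline?** Partly. The pre-scan examination notes abnormalities and maps the surface. No record is specified between that examination and the first probe contact, so only a change arising in that interval would be ambiguous.

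**3. How many contacts are involved?** Methods and Procedures gives 4 + 2 = 6 measurements per woman, or 6 × 10 = 60 in all. Subjects gives 2 per woman, or 2 × 10 = 20. The two sections are not reconciled. The gap exists under either count.

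**4. Illustration of why detection matters with 10 women.** Let p be the true proportion of women with a local injury and s the fraction of injuries that are recorded. Both are assumed, because the documents give neither. Women are taken as independent.

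Chance of recording at least one injury = 1 − (1 − p·s)^10:

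| p (assumed) | s = 1 | s = 0.5 |
|---|---|---|
| 10% | 1 − 0.90^10 = 65.1% | 1 − 0.95^10 = 40.1% |
| 1% | 1 − 0.99^10 = 9.6% | 1 − 0.995^10 = 4.9% |
| 0.1% | 1 − 0.999^10 = 1.0% | 1 − 0.9995^10 = 0.5% |

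One-sided 95% upper bound on p after 0 of 10 recorded = (1 − 0.05^(1/10)) / s = 25.9% / s:
- s = 1: 25.9%
- s = 0.75: 34.5%
- s = 0.5: 51.8%
- s = 0.25: above 100%, so uninformative

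Inspection matters for how 0 of 10 can be read. At low true rates it changes little in what 10 women are likely to show.

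**The case against.** The strongest case on the other side has four parts.

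**The cervix is in view.** The speculum is in place throughout, and the operator places the probe at four positions and returns to two of them. Visible bleeding or a lesion could be seen, logged and reported as an adverse event. This stands. A reader might infer from the procedure that injury will go undetected and be counted as safe. The documents do not support that: they leave room for chance detection, and the link to a safe result is an inference from an undefined end point. What remains is that an unprompted, unrecorded view does not show that anyone looked.

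**The chart covers appearance and the pre-scan examination maps the cervix.** This also stands. It would be wrong to say that appearance is charted only before the scan, or that a later lesion could not be attributed at all. The chart's timing is not stated, and the CRF itself is not among the documents. But no section asks for an entry on appearance after contact.

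**The risk is described as extremely rare.** With true rates of 1% or less, sample size limits the study more than detection does, as the table shows. This is a fair limit on the size of the concern. It does not remove the concern, because the study exists to assess the risk rather than to assume it.

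**This is a pilot whose procedure is expected to be refined in use.** That is a reason to keep the change small. It also means that a small change to the steps is in keeping with the plan.

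**Conclusion.** The point holds in a limited form. The protocol names tissue damage as a risk and makes safety its first objective and first end point, but specifies no inspection of the contact sites and relies on passive capture after the scan. Asymptomatic minor injury can go unrecorded, and a result of none recorded cannot be told apart from none sought.

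The size of the effect cannot be given. Any figure for the share of lesions missed would simply restate an assumed detection fraction, and the percentages above show direction only. The conclusion rests on the text as published and assumes that the CRF, which cannot be checked, adds no post-contact field. Nothing in the documents shows that injury is likely, or that the decision about pregnant women would change. This is a cheap improvement, not a flaw that prevents the study from running.

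**What to change.** In Methods and Procedures:
- **Step 1:** add that the appearance seen through the speculum is recorded on the existing CRF chart before the first probe contact.
- **Step 4:** separate the two removals. After the probe is withdrawn and before the speculum is removed, record whether any new visible change is present at the contacted sites (yes/no, and site).

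In Study End Points, report the number of women with any new change, out of the number inspected, under end point 1. How findings are graded, and their clinical meaning, is for the investigators to set.

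The sponsor should also reconcile the number of measurements per woman in Subjects with that in Methods and Procedures, so that the sites to be inspected are clear.

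**Cost:** wording in two sections, a few CRF fields and slightly longer speculum time. No extra visit, staff or instrument is needed.
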